### **Proportion of patients with positive influenza virus titer at each timepoint**

Proportion of patients positive for influenza virus titer will be presented by treatment at each visit and is defined as the percentage of patients whose influenza virus titer is not less than the lower limit of quantification ( $0.75 \log_{10} \text{TCID}_{50}/\text{mL}$ ) or positive among those assessed for influenza virus titer on Days 2, 4, 6, and 10.

Patients with a positive influenza virus titer on Day 1 will be included in this analysis.

### **Proportion of patients positive by RT-PCR at each time point**

Proportion of patients positive by RT-PCR will be presented by treatment at each visit is defined as the percentage of patients with detectable virus RNA ( $2.05$  for flu A and  $2.83$  for flu B  $\log_{10}$  virus particles/mL) among those assessed by RT-PCR on Days 2, 4, 6, and 10.

Patients with a positive by RT-PCR on Day 1 will be included in this analysis.

### **Area under the curve in virus titer**

Area under the curve (AUC) in virus titer will be presented by treatment group and will be calculated using the trapezoidal method. AUC of change from time 0 ( $t_0$ ) to time K ( $t_k$ ) is given by the formula

$$\sum_{k=1}^K \frac{(y_k + y_{k-1} - 2y_0)(t_k - t_{k-1})}{2}$$

where  $t_k$  (hours) represents the date of the  $k^{\text{th}}$  viral titer assessment ( $k = 0, \dots, K$ ) and  $y_k$  represents the  $\log_{10}$  value of the  $k^{\text{th}}$  viral titer assessment ( $\text{TCID}_{50}/\text{mL}$ ).

24-hours of time will be converted into one day. Patients with a positive virus titer on Day 1 will be subjected to this analysis. The lower limit is defined as  $0.75 \log_{10} \text{TCID}_{50}/\text{mL}$  for flu A and  $0.75 \log_{10} \text{TCID}_{50}/\text{mL}$  for flu B ( $\text{TCID}_{50}/\text{mL}$ ). If a patient is infected with multiple virus types, the sum of those virus titers will be used for analysis.

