The median time to cessation of viral shedding determined by virus titer was 24 hours in the baloxavir marboxil group compared with 96 hours in the placebo group. The difference in the time to cessation of virus shedding was 72 hours between the groups (p<0.0001). A significant difference in the median time to cessation of viral shedding of 48 hours (p<0.0001) was found also in comparison between the baloxavir marboxil (24 hours) group and the oseltamivir group (72 hours). In addition, baloxavir marboxil rapidly and significantly reduced the proportion of patients with positive influenza virus titer from Days 2 through 5 compared with that in the placebo group. Also, when

compared with the oseltamivir group, the proportion of patients with positive influenza virus titer decreased significantly in the baloxavir marboxil group.

Beneficial effects of baloxavir marboxil on fever were also demonstrated. The proportion of patients who had fever was reduced more rapidly in the baloxavir marboxil group than in the placebo group following the study drug administration. The median time to resolution of fever was shortened by 17.5 hours in the baloxavir marboxil group compared with the placebo group.

No deaths were reported in any groups. Two serious adverse events (viral meningitis and incarcerated inguinal hernia) were reported in 2 of 610 patients (0.3%) in the baloxavir marboxil group. The events resolved and were considered not related to study drug. Nine adverse events leading to withdrawal of study drug were reported: 3 events in 2 of 610 patients (0.3%) in the baloxavir marboxil group, 4 events in 1 of 309 patients (0.3%) in the placebo group, and 2 events in 2 of 513 patients (0.4%) in the oseltamivir group.

All of the adverse events leading to withdrawal of study drug in the baloxavir marboxil group were considered not related to the study drug. Adverse events were reported in 126 of 610 patients (20.7%, 172 events) in the baloxavir marboxil group, 76 of 309 patients (24.6%, 118 events) in the placebo group, and 127 of 513 patients (24.8%, 179 events) in the oseltamivir group. No statistically significant difference was found in the incidence between the baloxavir marboxil group and the placebo group (the Fisher's exact test, two-sided p-value=0.1781) or between the baloxavir marboxil group and the oseltamivir group (p=0.1146).

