### **2.2.4 Virology (Secondary) Endpoints**

- Time to cessation of viral shedding by virus titer and by reverse transcriptase-polymerase chain reaction (RT-PCR)
- Change from baseline in influenza virus titer and in the amount of virus RNA (RT-PCR) at each time point
- Proportion of patients with positive influenza virus titer and proportion of patients positive by RT-PCR at each time point
- Area under the curve in virus titer and in the amount of virus RNA (RT-PCR)

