## **2.3 DETERMINATION OF SAMPLE SIZE**

No formal sample-size calculations have been performed. Approximately 120 pediatric patients (80 patients in the baloxavir marboxil treatment group and 40 patients in the oseltamivir treatment group) will be enrolled.

To detect adverse events with a 3% incidence for at least 1 patient with a probability of  $\geq 90\%$ , the study will require 80 patients exposed to baloxavir marboxil. The given sample size provides a probability of at least 1 patient experiencing an adverse event with a true incidence rate of from 1% to 5% as shown in [Table 1](#).

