#### **4.6 EFFICACY ANALYSIS**

The statistical analyses of efficacy endpoints will be descriptive. The ITTi population will be used for all analyses. Additional analysis of efficacy analysis presenting the ITT population will not be completed.

The data will be summarized using means, standard deviations, medians, and ranges for continuous variables and proportions for categorical variables, as appropriate. Time-to-event endpoints and duration endpoints will be summarized using Kaplan-Meier plots and summaries of the median survival time. Summaries will be presented by treatment group.

Efficacy endpoints are based on the CARIFS questionnaire data which is recorded by parent/ caregiver using handheld device. This assessment data should be recorded for the following time periods:

Period	Time
Morning	0.500-10.59
Noon	11.00-14.59
Evening	15.00-18.59
Bedtime	19.00-23.59

\*data should not be recorded between 00.00 and 4.59.

In the case where the recorded time of an assessment is outside the period time window for that assessment, the end time of the period should be imputed as the assessment time.

In the case where the assessment time falls into the period between 00.00 and 4.59 (due to technical error) the assessment date will be imputed to the date prior to recorded assessment date and the assessment time will be imputed to the end time of the period time window.

The imputation method used in the derivation of time to alleviation of influenza signs and symptoms is described in Section 4.6.1. No further imputation methods will be used.

In all time to event analysis, patients who withdraw prior to event of interest will be censored at the last observation timepoint.

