### **Change from baseline in influenza virus titer at each time point**

Change from baseline in influenza virus titer ( $\log_{10}$ TCID50/ML) will be presented by treatment and is defined as the change from baseline in influenza virus titer on Days 2, 4, 6, and 10. If influenza virus titer is less than the lower limit of quantification, the virus titer will be imputed as 0.749 ( $\log_{10}$ TCID50/mL).

Only patients with a positive virus titer on Day 1 will be included in this analysis.

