### **Area under the curve in the amount of virus RNA (RT-PCR)**

AUC in virus RNA (RT-PCR) will be presented by treatment group and is defined as AUC of change from baseline in the amount of virus RNA (RT-PCR) from Day 1 to Day 10. AUC is calculated using the trapezoidal method similar to AUC in virus titer. Patients with a positive RT-PCR result on Day 1 will be subjected to this analysis. The lower limit of quantification is defined as  $2.18$  for flu A and  $2.93$  for flu B ( $\log_{10}$  virus particles/mL). If a patient is infected with multiple virus types, the sum of those the amount of virus RNA will be used for analysis.

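### For infectious titer, the SAP's AUC of change and its later change-from-baseline tables largely reflect baseline load, which adds avoidable noise to the by-arm comparison

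*SAP*

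**What the plan says.** SAP 2.2.4 lists the endpoint as "Area under the curve in virus titer and in the amount of virus RNA (RT-PCR"), and Protocol Table 1 does the same. SAP 4.6.2 then defines the titer version as the "AUC of change from time 0", using a trapezoid whose terms each subtract twice the baseline value. It gives no end day. The RNA version "is defined as AUC of change from baseline in the amount of virus RNA (RT-PCR) from Day 1 to Day 10".

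Titer change is tabulated on Days 2, 4, 6 and 10, with this rule: "If influenza virus titer is less than the lower limit of quantification, the virus titer will be imputed as 0.749" log10 TCID50/mL. RNA values below quantification are set to 2.18 (flu A) or 2.93 (flu B). The change and AUC analyses use only children positive on Day 1 by the relevant assay.

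SAP 4.6 states: "The statistical analyses of efficacy endpoints will be descriptive". No between-arm estimate, interval or baseline covariate is planned for virology. SAP 2.3 says "No formal sample-size calculations have been performed" and plans "80 patients in the baloxavir marboxil treatment group and 40 patients in the oseltamivir treatment group".

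**The concern.** Subtracting baseline helps when later values track it closely. Infectious titer in treated influenza falls quickly to the assay limit. Once there, a child's change is 0.749 minus his or her own baseline, which carries no information about how the drug worked in that child beyond the fact of clearance. Multiplying that baseline by many hours in an AUC amplifies it.

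The secondary virology objective is activity compared with oseltamivir, and Protocol 1.3 cites apparently greater antiviral efficacy as part of the rationale. Readers will therefore set the two arms' tables side by side. With at most about 40 controls, a chance difference in baseline load can visibly shift the AUC and the late change tables, and nothing in the plan shows or corrects for it.

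**Working it through.** **The plan's own figure.** The only size or precision figure is the adverse-event table in SAP 2.3. At a 3% rate, 1 - 0.97^80 = 91.3%, which reproduces. It has no bearing on virology, for which no precision is stated.

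**Weight on baseline (algebra only).** Swabs on Days 1, 2, 4, 6 and 10 are at 0, 24, 72, 120 and 216 h. Trapezoid weights are 12, 36, 48, 72 and 48 h, which sum to 216. Hence AUC of change = AUC - 216·y0, and the net coefficient of y0 is 12 - 216 = -204 h. The largest later weight is 72 h. RNA has the same weights. Expressing time in days rescales everything by 24 and changes no ratio.

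**How soon titers reach the floor.** Protocol 1.2.2 gives median titer cessation in a "comparison between the baloxavir marboxil (24 hours) group and the oseltamivir group (72 hours"). That study enrolled ages 12 to 64, and oseltamivir was given only from age 20. The paediatric study in Protocol 1.2.3 reports a mean Day 2 titer change of -4.20, which with the same floor needs a mean baseline of at least 0.749 + 4.20 = 4.95. No paediatric fraction below quantification is given. Exponential clearance with those medians, 1 - 2^(-t/median), gives the first two rows below.

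**Simulation.** Assumed, because the documents give no values: baseline mean 5 log10, baseline SD 1 to 2, SD of later underlying titers 1.5 to 2, baseline-to-later correlation 0 to 0.6, allocation 2:1. Entries in the last two rows are median (range) over that grid.

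| Titer | Day 2 | Day 4 | Day 6 | Day 10 | AUC |
|---|---|---|---|---|---|
| At floor, baloxavir | 50% | 88% | 97% | 99.8% | |
| At floor, oseltamivir | 21% | 50% | 69% | 88% | |
| Within-arm variance of change explained by baseline | 53% (6–78) | 81% (49–92) | 91% (75–96) | 98% (93–99) | 92% (73–97) |
| Variance of arm difference, adjusted / change | 0.56 (0.26–0.99) | 0.29 (0.13–0.74) | 0.16 (0.07–0.45) | 0.05 (0.02–0.13) | 0.13 (0.05–0.46) |

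For the AUC the median SE ratio is √0.13 = 0.36. With slower clearance (medians 48 and 96 h), baseline still explains 85% (49–94) of the AUC-of-change variance, and the SE ratio is 0.45 (0.29–0.81).

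**Absolute size for the titer AUC.** Assume 50 versus 25 children are titer-positive on Day 1. As a hand check, if every child were at the floor from Day 2, the SE of the arm difference would come from baseline alone: 204 × SD × √(1/50 + 1/25) = 50 × SD, or 50 to 100 log10·h for SD 1 to 2. One simulation matched to the 24 h and 72 h medians gave these SEs:

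| Baseline SD | AUC of change | Plain AUC | Baseline-adjusted |
|---|---|---|---|
| 1.0 | 44 | 31 | 26 |
| 1.5 | 60 | 40 | 30 |
| 2.0 | 74 | 50 | 35 |

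Other clearance models with the same medians widen the ranges to about 41–94 for AUC of change and 25–42 adjusted. At SD 1.5 the simulated arm difference was about -103 log10·h. As 103/60 = 1.7, the sign would be wrong in about 4 to 5% of trials; as 103/30 = 3.4, in under 0.1% after adjustment.

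**RNA.** The mean Day 2 change in the paediatric study was only -1.75, so early flooring is not shown. Off the floor, with equal SDs and correlation r, adjusted variance / change variance = (1 + r)/2: 0.50 at r = 0, 0.65 at r = 0.3 and 0.80 at r = 0.6. Adjustment then cuts variance by 20 to 50%.

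**The case against.** The strongest reply is that the analysis is descriptive, with no virology test or interval, so no planned inference is damaged. Protocol 6.7 leaves the detail to the SAP. Time to cessation and proportion positive, each by titer and by RT-PCR, subtract no baseline and show clearance by arm directly. The floor premise is borrowed from adults and adolescents. A common-slope linear model is only an approximation when the arms differ in the share held at a constant, and model-based intervals add inferential output to a descriptive plan.

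Much of this stands, and it limits the point to the change and AUC endpoints. The descriptive label does not dispose of it: the objective is comparative, the arms will be compared by eye, and the noise can be removed with data already collected. The model's imperfect fit is a reason for robust standard errors, not for leaving baseline out.

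A reader might infer more than the documents support:

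- **That the comparison is biased.** Block randomisation balances baseline in expectation, and the expected arm difference is unchanged.
- **That most children in both arms are at the floor by Day 4.** The adult median puts only about half of oseltamivir children there.
- **That the tables show no drug effect.** A high within-arm share of variance due to baseline is not an absent effect between arms.
- **That baseline is one swab.** The schedule of activities requires at least two at each visit.

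**Conclusion.** The point holds for infectious titer. The AUC as computed, the Day 6 and Day 10 change tables and, less strongly, the Day 4 table mainly reflect baseline load. The -204 h weight is exact for the scheduled swab times. The size of the loss depends on assumptions: the SE of the titer AUC arm difference is about 41–94 log10·h as planned against about 25–42 adjusted, a ratio of roughly 0.3 to 0.8. This rests on baseline SD 1–2 log10, 50 versus 25 evaluable children and adult and adolescent clearance times.

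No single figure, such as half the precision, describes it: on Day 2 the gain runs from almost none to substantial, while on Day 10 over 85% of the variance of the change difference is avoidable. For RNA only the formula's weight and the modest off-floor gain carry over. The consequence is a noisier descriptive comparison, open to chance baseline imbalance.

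**What to change.** In SAP 4.6.2:

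1. Report the AUC of log10 titer and of RNA over a fixed Day 1 to Day 10 interval, matching the endpoint's wording. State the end day for titer and how a last swab away from Day 10 is handled, since SAP 4.4 accepts Days 8 to 12 for Visit 5.
2. Add a between-arm difference with 95% CI for the AUC and for Days 2 and 4, from a linear model with arm and baseline log10 value, and virus type as well for RNA because its floors differ. Use robust standard errors and label the results descriptive.
3. Keep the raw change tables as supportive.

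Step 1 alone recovers only part of the loss (SE 60 to 40 at SD 1.5, against 30 with adjustment). With a common end day and baseline in the model, AUC and AUC of change differ only by 216·y0 and give the same adjusted arm difference, so nothing in the planned summary is lost. The cost is SAP wording and a few extra models and intervals in a descriptive plan. No new data are needed.

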### **Area under the curve in the amount of virus RNA (RT-PCR)**

AUC in virus RNA (RT-PCR) will be presented by treatment group and is defined as AUC of change from baseline in the amount of virus RNA (RT-PCR) from Day 1 to Day 10. AUC is calculated using the trapezoidal method similar to AUC in virus titer. Patients with a positive RT-PCR result on Day 1 will be subjected to this analysis. The lower limit of quantification is defined as  $2.18$  for flu A and  $2.93$  for flu B ( $\log_{10}$  virus particles/mL). If a patient is infected with multiple virus types, the sum of those the amount of virus RNA will be used for analysis.

### **4.6.3 Exploratory Endpoints**

#### **Polymorphic and treatment-emergent amino acid substitutions in the PA, PB1, and PB2 genes**

Sequencing of PB1 and PB2 will be done for:

- baseline viruses with reduced susceptibility to baloxavir (fold-change in  $\text{EC}_{50} > 10$  for type A viruses and  $> 5$  for type B viruses compared to reference virus in phenotypic assay).

- viruses (baseline and last evaluable timepoint) without amino acid substitution in PA, but with reduced response to treatment or with virus rebound.

These will be defined according to the following criteria below. If an amino acid substitution is detected, an additional intermediate timepoint sample will be sequenced.

	Criteria
1) Subjects who exhibit viral titer rebound:	Viral titer at [(a certain time point) – (just before time point)] $\geq 2 \times$ SD value of viral titer of control virus in assay * * [REDACTED] [REDACTED] [REDACTED]
2) Subjects who continue to shed virus at Day 6 and beyond:	Viral titer (log 10 TCID 50 /mL) at Day 6 and beyond > 1.5
3) Subjects who do not show a reduction in virus titer:	Viral titer (log 10 TCID 50 /mL) at a certain time point: A > 1.5 Viral titer (log 10 TCID 50 /mL) at just before time point: B > 1.5 AND Viral titer (log 10 TCID 50 /mL) at [(a certain time point: A) - (just before time point: B)] $\geq 0$

**Drug susceptibility in patients with evaluable virus**

**Non-compartmental PK parameters (intensive PK)**

Analysis methods for exploratory analysis will be described in a separate PK plan/report.

**4.6.4 Subgroup Analyses**

Subgroup analysis of the following secondary endpoints, based on virus type and subtype, will be conducted:

- Time to alleviation of influenza signs and symptoms
- Time to cessation of viral shedding by RT-PCR
- Time to cessation of viral shedding by virus titer

## 4.7 PHARMACOKINETIC AND PHARMACODYNAMIC ANALYSES

The PKEP population will be used for all analyses.

For patients with blood samples collected, individual plasma baloxavir marboxil and S-033447 concentrations will be tabulated by patient and by timepoint. Individual and mean (if appropriate) plasma baloxavir marboxil and S-033447 concentrations versus time data will be plotted by defined body-weight groups (e.g., 5–10 kg, 10–15 kg, etc.). The  $C_{24}$  and  $C_{72}$  of S-033447 will be listed and summarized (mean, standard deviation, coefficient of variation, median, minimum, and maximum) by defined body-weight group.

Additional PK analyses may be conducted as appropriate. For example, for patients undergoing intensive PK assessments ([Appendix 3](#)), individual PK parameters of baloxavir marboxil and S-033447 (AUC,  $C_{max}$ , time to maximum plasma concentration, and terminal half-life) may be calculated using model-independent methods, as applicable (if sufficient data available for reliable AUC estimates). Parameters will be listed and if deemed useful, summarized (mean, standard deviation, coefficient of variation, median, minimum, and maximum) by defined body-weight group.

In addition, non-linear mixed-effects model (NONMEM, Version 7.3 or higher) will be used to analyze the PK data. The population typical PK parameters (e.g., apparent clearance, apparent volume of distribution for the central compartment) and their covariates will be estimated. Individual PK metrics, such as area under the concentration-time curve from Time 0 to infinity ( $AUC_{inf}$ ),  $C_{24}$ ,  $C_{72}$ , and  $C_{max}$ , will be also calculated using post hoc Bayesian estimation for each patient, and plotted against significant covariates identified (e.g., body weight, age). The derived individual values will be plotted against body weight and age. PK parameters will be tabulated and summarized (i.e., by mean, standard deviation, coefficient of variation, median, and minimum and maximum) by age group. PK exposure and response (e.g., virus titers) relationships will be explored. Details related to the Population PK analyses and downstream PK exposure-response analyses will be provided in a dedicated modelling and simulation plan, and results obtained in dedicated M&S reports.

Pediatric exposure matching to adults will use  $C_{24}$  (observed, as well as Bayesian post hoc) as a primary PK parameter. Key secondary PK metrics, such as  $C_{72}$  and  $AUC_{inf}$  (derived as Bayesian post hoc), will assess whether exposure is sustained similarly as in adults, and to explore whether or not viral rebound, if any, may be associated with lower  $C_{72}$  values. For completeness,  $C_{max}$  will be calculated as secondary PK parameter. Assessment of pediatric exposure and comparison to adults will use all PK data (sparse and intensive PK). Results may be described within the population PK report or in a dedicated extrapolation report.

#### **4.8 MISSING DATA**

In safety analyses, all deaths are included, from all sources, regardless of completeness of death date; patients who died with only a partial death date available will be included. Partial dates for AEs, concomitant medications, laboratory assessments, and medical history will be imputed following a conservative approach.

In efficacy analyses, a death is considered an event if and only if a complete death date is available; patients who died with only a partial death date available will be censored.

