#### **4.6.1            Efficacy Endpoints (Secondary Objectives)**

##### **Time to alleviation of influenza signs and symptoms**

Time to alleviation (TTAS) of influenza signs and symptoms in hours, will be summarized using descriptive statistics by treatment, as well as Kaplan-Meier plots. It is defined as the length of time taken from the start of treatment to the point at which all of the following criteria are met and remain so for at least 21.5 hours:

- A score of 0 (no problem) or 1 (minor problem) for cough and nasal symptoms (items 14 and 15 of the CARIFS questionnaire - see [Appendix 4](#))
- A “yes” response to the following question on the CARIFS: “Since the last assessment has the subject been able to return to day care/school, or resume his or her normal daily activity in the same way as performed prior to developing the flu?”
- First return to afebrile state (tympanic temperature  $\leq 37.2^{\circ}\text{C}$ ).

If a score of 4 (“do not know” or “not applicable”) occurs at any assessment during the study for items 14 or 15, the assessment will not be included in the calculation of the alleviation of symptoms because the assessment was unobservable.

Patients with symptom scores  $\leq 1$  for both items 14 and 15, as well as tympanic temperature  $\leq 37.2^{\circ}\text{C}$  and a “yes” response to the question ‘Since the last assessment has the subject been able to return to day care/school, or resume his or her normal daily activity in the same way as performed prior to developing the flu?’ at baseline will have a TTAS of all symptoms set to missing.

Patients who do not experience alleviation of symptoms prior to completion or withdrawal from study will be censored at the last observation time point.

Baseline is defined as the first CARIFS assessment after start of treatment on Day 1.

The number of patients with completed CARIFS as well as the number with missing CARIFS per assessment, will be presented by treatment. Additionally, the number and percentage of those with ‘Don’t Know/ Not Applicable’ per Question per assessment will be presented by treatment.

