##### **Duration of fever**

Duration of fever will be summarized using descriptive statistics by treatment, as well as Kaplan-Meier plots. It is defined as the time to return to afebrile state [tympanic temperature  $\leq 37.2^{\circ}\text{C}$ ] and remaining so for at least 21.5 hours.

Patients who do not return to afebrile state will be censored at the last observation time point.

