## **Duration of symptoms**

Duration of symptoms will be summarized using descriptive statistics by treatment, as well as Kaplan-Meier plots. Duration of symptoms is defined as alleviation of all symptoms as defined by a score of 0 [no problem] or 1 [minor problem] and remaining so for at least 21.5 hours, for all 18 symptoms specified in the CARIFS questionnaire.

If a score of 4 (“do not know” or “not applicable”) occurs at any assessment during the study for any item, with the exception of items 10, 11 and 12 the assessment will not be included in the calculation of the alleviation of symptoms because the assessment was unobservable.

However, if a score of 4 occurs for items 10, 11 or 12, the assessment will be included, with a score of missing for these items.

In addition, duration of individual symptoms will be summarized using descriptive statistics by treatment, as supportive analysis. Patients who have an individual symptom score  $\leq 1$  at baseline will have the duration of that symptom set to missing.

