## **Time to return to normal health and activity**

Time to return to normal health and activity will be summarized using descriptive statistics by treatment, as well as Kaplan-Meier plots.

‘Normal health and activity’ is identified by a ‘Yes’ response to the following question on the CARIFS: “Since the last assessment has the patient been able to return to day care/school, or resume his or her normal daily activity in the same way as performed prior to developing the flu?”

Patients who do not return to normal health and activity will be censored at the last observation time point.

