## **4.6.2 Virology (Secondary) Endpoints**

### **Time to cessation of viral shedding by virus titer**

Time to cessation of viral shedding by virus titer is defined as the time, in hours, between the initiation of any study treatment and first time when the influenza virus titer is below the limit of detection. Patients whose virus titers have not reached the limit by the last observation time point will be treated as censored at that time point. One day is converted into 24 hours.

Patients with a positive virus titer on Day 1 will be included in this analysis.

This endpoint will be summarized using descriptive statistics by treatment, as well as Kaplan-Meier plots.

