### **Time to cessation of viral shedding by RT-PCR**

Time to cessation of viral shedding by RT-PCR, in hours, is defined as the time between the initiation of any study treatment and first time when the virus RNA by RT-PCR is below the limit of detection. Patients whose virus RNA have not reached the limit by the last observation time point will be treated as censored at that time point. For the patients with multiple virus types, this endpoint is defined as the time between the initiation of the study treatment and first time when the virus RNA by RT-PCR is below the limit of detection for all virus types. One day is converted into 24 hours.

Patients with a positive virus RNA on Day 1 will be included in this analysis.

This endpoint will be summarized using descriptive statistics by treatment, as well as Kaplan-Meier plots.

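### SAP 4.8 counts a fully dated death as an event in efficacy analyses, although the event in all six time-to-event endpoints is recovery or viral clearance

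*SAP*

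**What the plan says.** SAP 4.8 (Missing Data) sets a rule for deaths in efficacy analyses: "In efficacy analyses, a death is considered an event if and only if a complete death date is available". When the date is incomplete, the coding is reversed: "patients who died with only a partial death date available will be censored". No endpoint is named.

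SAP 4.6.1 and 4.6.2 define six endpoints that are summarized with Kaplan-Meier plots. Their rules are as follows.

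- Alleviation of signs and symptoms has this rule: "Patients who do not experience alleviation of symptoms prior to completion or withdrawal from study will be censored at the last observation time point" (SAP 4.6.1).
- Fever has a similar one: "Patients who do not return to afebrile state will be censored at the last observation time point" (same section).
- The symptom-duration endpoint has no censoring sentence. Its text offers a definition, which begins "Duration of symptoms is defined as alleviation of all symptoms", with a 21.5-hour hold.
- Return to normal activity is handled like fever: "Patients who do not return to normal health and activity will be censored at the last observation time point" (also SAP 4.6.1).
- Shedding by titer has its own wording: "Patients whose virus titers have not reached the limit by the last observation time point will be treated as censored at that time point" (SAP 4.6.2).
- Shedding by RT-PCR follows the same pattern: "Patients whose virus RNA have not reached the limit by the last observation time point will be treated as censored at that time point" (also SAP 4.6.2).

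The general sentence in SAP 4.6 censors patients who withdraw before the event at their last observation. It mentions neither deaths nor patients who complete the study without the event. Protocol 4.6.2 gives an open-ended list of reasons for withdrawal, and death is not among them.

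**The concern.** Counting death as an event suits an endpoint whose event is bad. Here every time-to-event endpoint measures how quickly a good outcome arrives. Under 4.8, a child who dies unrecovered with a known date of death would enter the curve as alleviated, afebrile, back to normal activity or clear of virus on that date. A child with the same course but an incomplete date would be censored.

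The endpoint sections lead to a different result, and the SAP does not say which text prevails. Two programmers could each follow the SAP and code the same death differently. Under one coding, a death would improve the arm's result on the key secondary efficacy endpoint.

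Duration of symptoms is the weakest spot. For that endpoint 4.8 is the only sentence that expressly addresses death, and no sentence covers a completer who never recovers. The second gap does not depend on any death.

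**Working it through.** The documents give no figure for this point. The only sample-size figures (the adverse-event probabilities in SAP Table 1) do not bear on it. The check is a comparison of the rules, followed by the size of the effect.

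**Comparison of the rules.** There are six time-to-event endpoints. The event is favourable in 6 of 6, and none lists death as an event. Five of the six have their own censoring sentence; duration of symptoms is the exception. Death cannot satisfy any of the definitions: they need symptom scores or temperature sustained for 21.5 hours, a positive answer on return to activity, or a titer or RNA result below the limit of detection.

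**Effect of one death.** Inputs: planned arms of 80 (baloxavir marboxil) and 40 (oseltamivir), from SAP 2.3. Assumptions: the death precedes all recoveries in its arm, nothing else is censored, and *m* recoveries follow in an arm of size *n*. The Kaplan-Meier proportion not yet recovered is:

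- death coded as an event: S = (n − 1 − m)/n
- death censored at the last observation: S = (n − 1 − m)/(n − 1)
- gap: (n − 1 − m)/[n(n − 1)], which is 1/n at *m* = 0 and shrinks as *m* grows

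The documents give no expected influenza-infected (ITTi) share. The first two rows below take it as 100% of enrolled patients. The last two assume 60% (0.6 × 40 = 24 and 0.6 × 80 = 48).

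| n | Gap at death | S when m = n/2: event vs censored | Gap then | Recovery at which S ≤ 0.5: event vs censored |
|---|---|---|---|---|
| 40 | 2.5 points | 19/40 = 0.475 vs 19/39 = 0.487 | 1.2 points | 19th vs 20th |
| 80 | 1.25 points | 39/80 = 0.4875 vs 39/79 = 0.494 | 0.6 points | 39th vs 40th |
| 24 | 4.2 points | 11/24 = 0.458 vs 11/23 = 0.478 | 2.0 points | 11th vs 12th |
| 48 | 2.1 points | 23/48 = 0.479 vs 23/47 = 0.489 | 1.0 points | 23rd vs 24th |

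**In hours, for illustration only.** Assume exponential recovery times with a median of 44.6 h (the earlier pediatric study, Protocol 1.2.3) or 53.7 h (the adult and adolescent study, Protocol 1.2.2), and one death at 24 h.

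- Arm of 40: the median is 41.4 h with event coding against 44.6 h censored, or 49.8 against 53.7 h. The differences are 3.2 and 3.9 h.
- Arm of 80: 43.0 against 44.6 h, or 51.8 against 53.7 h. The differences are 1.6 and 1.9 h.
- A death at 48 h with an assumed median of 44.6 h leaves the median unchanged.

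**How likely a death is.** The three earlier studies summarized in the protocol report no deaths among 400 + 1,432 + 107 = 1,939 patients. The one-sided 95% upper bound on the risk is 1 − 0.05^(1/1939) = 0.15%. At that bound, the chance of any death among 120 patients is 1 − (1 − 0.00154)^120, about 17%. This pools adults with children. The pediatric study alone (0 of 107) has an upper bound of 2.8%, so it says little by itself.

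**The case against.** There are five arguments on the other side.

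- **Death may already count as withdrawal.** SAP 2.4 and the alleviation section treat withdrawal and completion as the only two exits, so the general sentence in 4.6 might already censor deaths. That is a reasonable reading, but it puts 4.6 in direct conflict with 4.8.
- **The definitions block the harmful reading.** Death cannot meet any endpoint's criteria, and 4.6 rules out imputation beyond the stated method. A careful programmer might therefore never code a death as recovery. This lowers the risk, but 4.8 still instructs the opposite and no order of precedence is stated.
- **4.8 may have been written for complications.** Influenza-related complications do include death. That endpoint is a count and a percentage with no censoring, so the second half of the 4.8 sentence can only refer to time-to-event endpoints.
- **The remedy is not free of bias.** In the example with n = 40 and 20 recoveries, the true proportion unrecovered is 20/40 = 0.500. Event coding gives 0.475 and censoring at the last observation gives 0.487, so recovery is still overstated by 1.3 points. Censoring at the end of scheduled observation would give 0.500. This stands. Censoring at the last observation moves in the right direction and matches the rule the SAP already uses, but it is not the only defensible choice.
- **It will hardly ever matter.** Illness requiring inpatient treatment is excluded, the earlier studies had no deaths, and efficacy is descriptive, so no test or error rate is affected. SAP 4.5.2 lists and tabulates deaths, and 4.8 keeps every death in the safety analyses whatever its date. This also stands, and it limits the importance of the point.

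**Conclusion.** The concern holds. As written, the efficacy sentence in SAP 4.8 is wrong for all six time-to-event endpoints and conflicts with the censoring rules of five of them. The sixth, duration of symptoms, has no clear rule for a dated death other than 4.8, and none for a completer who never recovers.

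The expected impact is low, because the error takes effect only if a child in the ITTi population dies before recovering. With one such death, all enrolled patients in the ITTi population and no other censoring, the two codings differ by at most 2.5 points (arm of 40) or 1.25 points (arm of 80), and the median moves by at most one ordered recovery time. With an assumed 60% ITTi share, the largest gaps are 4.2 and 2.1 points. The sentence should be corrected because it gives the wrong answer in the one case it governs, and correcting it costs almost nothing.

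**What to change.** Make two text changes.

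1. In SAP 4.8, replace the efficacy sentence with: *Death is not an event in any time-to-recovery or time-to-cessation-of-shedding endpoint. A patient who dies before the event is censored at the last observation, as in Sections 4.6 to 4.6.2, however complete the death date is.*
2. In SAP 4.6, extend the general censoring sentence to: *In every time-to-event analysis, a patient who withdraws, dies or completes the study without the event is censored at the last observation.*

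This agrees with the five endpoint sentences as they stand and closes both gaps for duration of symptoms. The complications count is unaffected: it is not a time-to-event endpoint and still counts death as an outcome.

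If a death occurs, an optional sensitivity analysis can censor it at the end of scheduled observation, which removes the remaining optimism shown above. Making that the main rule would require amending the five endpoint sentences.

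The cost is one sentence replaced and one extended, with no new data and no change to the endpoint sections.
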